10.4.1. Treatment Emergent Adverse Events

- All AEs that occur during the trial after the subject has signed the informed consent are to be documented in the eCRF, regardless of whether they are reported by the subject, elicited by Investigator questioning, detected through physical examination, or by other means.

For adverse events of special interest see Section 10.6.

As far as possible, each AE is described by:

- Duration (start and end dates);
- Start/end of trial medication;
- Severity grade (mild, moderate, severe);
- Investigation causality (relationship to the trial product);
- Action(s) taken (concomitant medication, change of trial medication etc.) including start and end of respective action;
- Concomitant diseases and respective medication in general;
- Start, end and dosage of rescue medication;
- Outcome.

Definition of terms:

AE

An AE is any untoward medical occurrence (change in anatomical, physiological, or metabolic function) in a subject, which does not necessarily have any causal relationship with the product under investigation. An AE may be an exacerbation of a pre-existing medical condition that was present before the subject was assigned to a treatment group.

TEAE

Treatment emergent AEs (TEAEs) are those AEs occurring from time point of first ingestion of investigational product until last visit or any event already present that worsens in either intensity or frequency following exposure to the treatment.

SAE or TESAE

An SAE is any untoward medical occurrence that at any dose:

- Results in death;
- Is life-threatening (Note: the term “life-threatening” refers to an event in which the subject is at risk of death at the time of the event; it does not refer to an event which hypothetically may cause death if it is more severe);
- Requires subject hospitalization or prolongation of existing hospitalization (for the purpose of this trial, a hospitalization is defined as a hospital stay of at least 8 hours and/or an overnight stay);
- Results in persistent or significant disability/incapacity;
- Is a congenital anomaly/birth defect;
- Other medically important condition.

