## **2 STUDY OBJECTIVES AND ENDPOINTS**

### **2.1 Primary Objective and Endpoint**

To evaluate the general safety of treatment with Estetrol (E4) 20 mg.

Safety endpoints for primary objective #1

- Frequency of Treatment Emergent Adverse Event (TEAE) (including Serious Adverse Events [SAEs])
- Frequency of changes in results in physical and gynecological examinations, vital signs, electrocardiogram (ECG), mammography, and breast examination at each measured time point
- Frequency of changes in routine clinical laboratory tests results (hematology and chemistry) at each measured time point

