## **3 STUDY DESIGN**

### **3.1 General Study Design**

This study is a Phase III study, with multiple centers in the USA and Canada. Eligible subjects will be post-menopausal women,  $\geq 40$  up to  $\leq 65$  years of age, seeking treatment for relief of moderate to severe vasomotor symptoms (VMS) associated with menopause.

The Safety Study part will be conducted in approximately 200 hysterectomized and approximately 200 non-hysterectomized postmenopausal women, who are seeking treatment for the relief of VMS (condition clinically indicated by the investigator) associated with menopause and have at least 1 moderate to severe VMS symptom per week.

The Safety Study part is an open label study, to evaluate the effect of E4 20 mg (Arm 4) on the primary safety and secondary efficacy endpoints (lipid and glucose metabolism, HRQoL and TS) over a 52 week treatment period. For endometrial protection, all non-hysterectomized subjects will receive treatment with 200 mg progesterone (P4) once daily for 14 consecutive days, after completion of the E4 treatment. The target number of subjects to be included in the Safety Study part is approximately 400. Enrollment in the Safety Study part will stop as soon as the minimum required number of subjects in each study group and study part is enrolled.

[figure not shown]
At least 8 visits (up to 15 months) are planned in the Safety Study part, this includes:

- Washout visit (occurring generally up to 8 weeks prior to Screening visit),
- Screening visit (occurring 4 weeks prior to Baseline [Visit 1]),
- Treatment visits (occurring within 53 weeks; Visit 1 to Visit 6), include:
  - Baseline (Visit 1),
  - Five On-treatment visits (Visits 2, 3, 4, 5 and 6), the last treatment visit (Visit 6) is also the end of treatment (EoT) visit, which will also occur in case of early discontinuation.

For non-hysterectomized women an additional endometrial safety follow-up visit (visit 7) is planned approximately 10 days after completion of the 14 days of P4 treatment, which will also occur in case of early discontinuation

The trial schedule for Safety Study part is summarized in [Figure 1](#).

Figure 1: Trial Schedule

EoT = End of Treatment; NH = Non-hysterectomized; H = Hysterectomized; E4 = estetrol; P4 = progesterone

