At baseline (Visit 1), secondary efficacy assessments (lipid and glucose metabolism) will be performed and the MENQOL questionnaire will be completed. Subjects will visit the trial center after 4 weeks (Visit 2), 12 weeks (Visit 3), 6 months (Visit 4) and 9 months (Visit 5) of treatment for safety assessments, and for completion of the CGI questionnaire (Visit 2 only). At Visit 3, secondary efficacy assessments will also be performed and the MENQOL and CGI questionnaires will be completed. For non-hysterectomized subjects endometrial thickness will be assessed on visits 3, 4 and 5. During treatment non-hysterectomized subjects will record daily study drug intake and vaginal bleeding events in a paper diary. After 12 months of treatment subjects will visit the trial center for the EoT visit (Visit 6) during which secondary efficacy assessments and safety assessments will be performed, questionnaires will be completed and a mammography will be made. For non-hysterectomized subjects endometrial thickness will be assessed and, if they have completed at least 12 weeks of E4, an endometrial biopsy will be performed.

---

After the EoT procedures, all non-hysterectomized subjects will receive treatment with 200 mg P4 for 14 days. Approximately 10 days after completion of the progestin treatment, endometrial thickness will be measured (Visit 7).

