TEAE	AE Start Date known: TEAE if AE Start Date on or after Treatment Start Date and AE Start Date is before the date of the last visit where last visit is defined as end of treatment, early discontinuation or follow up visit (for NH subjects).  AE Start Date unknown: TEAE if AE Stop Date is on or after Treatment Start Date.
Baseline	
Baseline	Unless otherwise noted, Baseline is defined as the last non-missing value, including results from repeated and unscheduled measurements, prior to Treatment Start Date.
Change from Baseline	Date of interest – Baseline
Other	
TS	TS is the percentage of subjects in each category in CGI questionnaire (very much improved, much improved, minimally improved, no change, minimally worse, much worse, and very much worse) which will be presented at week 4, week 12 and week 52 for the different treatment group.

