#### 7.4.1.4 Prior and Concomitant Medications

Medications used in this study will be coded by using the latest available version of the World Health Organization (WHO) Drug Dictionary Enhanced (Enhanced 2019 March version, or higher).

**Prior medications:** A medication with a start date prior to Treatment Start Date.

**Concomitant medications:** A medication with a start date on or after Treatment Start Date.

If a medication start date is before the Treatment Start Date and is ongoing at Treatment Start Date, then the medication will be counted as both a prior and a concomitant medication.

Prior and concomitant medications will be summarized by anatomical therapeutic chemical (ATC) level 2 and preferred name (level 5) for the Safety Analysis Set. A listing of medication data will be produced for the Included Set.

Partial medication start and stop dates will be imputed as detailed in [Section 6.2.2](#).

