#### **7.7.1.13 Vaginal Bleeding and/or Spotting**

Absence or occurrence of vaginal bleeding and/or spotting on a daily basis will be assessed using the scale below:

- 0 = Absence of vaginal bleeding or spotting;
- 1 = Spotting: evidence of minimal blood loss requiring none or at most one pad, tampon or panty liner per day;
- 2 = Bleeding: evidence of blood loss requiring more than one pad, tampon or panty liner per day.

Frequency counts (n) and percentage of subjects with absence of any bleeding and/or spotting during the cycle, with vaginal bleeding and/or spotting during the cycle, with bleeding only during the cycle, with spotting only during the cycle will be provided for each 28- day cycle of treatment based on data in the subject diary (in non-hysterectomized subjects) for the Safety Analysis Set.

The number of days with bleeding or spotting, as reported on subject diaries, will be summarized by 28-day cycle of treatment.

A listing will be provided for vaginal bleeding and/or spotting and/or amenorrhea for the Included Set.

The following data will be excluded from analysis of endpoints for bleeding (to be analysed separately)

- bleeding for the day on which an endometrial biopsy was performed and 6 days after biopsy and
- bleeding reported after discontinuation of study drug (for example withdrawal bleeding, on P4 treatment)

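### Safety part: in women with a uterus, the TEAE window pools about 24 days on and after progesterone with E4 time, and no AE table separates the two

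*SAP*

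**What the plan says.** The Safety part is a single open-label arm whose primary objective is the general safety of E4 20 mg. Its first endpoint is "Frequency of Treatment Emergent Adverse Event (TEAE) (including Serious Adverse Events [SAEs" (SAP 2.1).

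SAP 6.1, Table 1, gives the counting rule for a known onset date: "TEAE if AE Start Date on or after Treatment Start Date and AE Start Date is before the date of the last visit". The same entry then settles which visit closes the window for each group of women: "last visit is defined as end of treatment, early discontinuation or follow up visit (for NH subjects". The protocol definition has the same end point: "from time point of first ingestion of investigational product until last visit" (Protocol 10.4.1).

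After E4, "all non-hysterectomized subjects will receive treatment with 200 mg progesterone (P4) once daily for 14 consecutive days, after completion of the E4 treatment" (SAP 3.1). The protocol synopsis and Protocol 8.3 extend this to women who stop early. The follow-up visit comes about 10 days after the P4 course, and AEs are recorded there (Protocol 10.1.6.7).

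For the diary bleeding endpoints the SAP takes a different line. It excludes, for separate analysis, "bleeding reported after discontinuation of study drug (for example withdrawal bleeding, on P4 treatment" (SAP 7.7.1.13), and the amenorrhea analysis makes the matching exclusion (SAP 7.7.1.14).

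AESIs, which include grade 2 bleeding, are defined as a subset of TEAEs. SAP 7.7.1.1 collects them until the follow-up visit, whereas Protocol 10.6 ends collection at the end-of-treatment (EoT) visit.

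**The concern.** A reader of the primary table will take it as the adverse event profile of E4 20 mg. In women with a uterus it also contains events that began on a second hormone or in the days after that hormone was withdrawn. This part has no comparator, so nothing else in its tables separates the two sources.

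The problem affects one stratum only. For hysterectomized women the window closes at EoT or early discontinuation. The overview, the AESI tables and the tables of reproductive-system and abdominal-pain events, all shown by hysterectomy status, thus place an E4-only window beside one that also holds P4 and post-P4 time.

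The SAP is also inconsistent with itself. A grade 2 bleed during the P4 course is kept out of the diary bleeding endpoint. The same bleed, if reported as an AE, enters the TEAE tables and, under the SAP's collection window, the AESI tables.

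**Working it through.** The plan states no figure that depends on this definition, so there is none to reproduce. The check traces the window and then the tables.

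**1. Length of the added period.** Inputs: 14 days of P4 and about 10 days to follow-up (SAP 3.1). 14 + 10 = 24 days.

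**2. Check against the visit windows** (SAP Appendix 1, Table 5: EoT Day 365–371, Visit 7 Day 379–392).
- Shortest gap: 379 − 371 = 8 days. Longest gap: 392 − 365 = 27 days.
- EoT on Day 365 to 368 puts the nominal Visit 7 on Day 389 to 392, inside its window. EoT on Day 371 puts it on Day 395, three days outside.
- So 24 days is the nominal value, not an exact one.

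**3. Share of a woman's TEAE window.**
- Completer: 24 / (371 + 24) = 6.1%, or 24 / (365 + 24) = 6.2%.
- Woman whose E4 ends on Day 35, the last day of the Visit 2 window: 24 / (35 + 24) = 40.7%.
- Protocol 8.1 anticipates 50% dropout by 12 months, so shorter windows will be common. These are shares of time, not estimates of bias.

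**4. How much of the period could still reflect E4.** Protocol 5.2 gives a half-life of about 28 hours. Taking five half-lives as a yardstick (my choice), 5 × 28 = 140 hours = 5.8 days. That leaves 24 − 5.8 = 18.2 days, or 76% of the period, beyond it. The first days may still carry E4 effects; most of the period lies later.

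**5. Who is affected.** At most about 200 of about 400 women (SAP 3.1), limited to those who take P4 and attend Visit 7. A woman without Visit 7 has EoT or early discontinuation as her last visit.

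**6. Is the period separated anywhere?** SAP 7.7.1.1 splits its TEAE and AESI tables by system organ class and preferred term, intensity, relationship and, for some, hysterectomy status. None is split by E4 period against P4/follow-up period. The AE listings carry a TEAE flag but no stated phase flag.

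**7. Effect on the reported rate.** Let p be the share of women with a uterus who have an event on E4, and q the share of the rest whose first event starts in the added period. The reported proportion is p + (1 − p)q, an excess of (1 − p)q over the E4 period alone. With two strata of about 200, the excess over all women is about half of that. The documents give neither p nor q, so no numerical effect follows.

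**The case against.** The best defence is that the SAP applies the protocol's own definition, that following AEs after the last dose is sound, and that treatment-emergent does not mean caused by E4. All of this stands, and it is why the overall tables should stay. It does not explain why the later period is never shown apart.

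A second defence is that P4-period bleeding will be analysed separately from the diary, and that the AE listings, AE start day and E4/P4 administration listing allow any event to be placed. This shows the data exist. It does not supply a tabulation for TEAEs or AESIs.

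Third, no formal comparison of the strata is planned (SAP 7.1, 7.7). That is correct, so no inferential error arises. The descriptive tables still set unequal windows side by side.

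Some stronger readings are tempting, but the documents do not support them:
- *P4-related events will be tabulated as related to E4.* Protocol 10.4.1, Table 5, grades causality to the investigational drug and classes the effect of another concurrent drug as not related. The synopsis lists P4 apart from the investigational product, and Protocol 9.3.1 names E4 as that product. SAP 7.5 uses *study drug* loosely for both in one listing. That leaves Treatment Stop Date in Table 1 unclear but does not show misattribution.
- *The bleeding or TEAE rate is inflated by a particular number of points.* No rate for the P4 period is given. Diary bleeding becomes a TEAE only if reported as an AE, and the two documents disagree on whether AESI reporting covers this period.
- *The open-ended concomitant-medication definition* ("A medication with a start date on or after Treatment Start Date") *distorts results.* No endpoint is shown to depend on it.

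**Conclusion.** The point holds as a gap in tabulation. For women with a uterus who take P4 and attend follow-up, about 24 nominal days on and after P4 are pooled with E4 time in the primary TEAE endpoint, the AESI tables and the tables by hysterectomy status. That is about 6% of a completer's window and a larger share for early stoppers. Hysterectomized women have no equivalent period. The SAP already accepts the separation for diary bleeding and does not carry it over to AEs.

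The conclusion rests on the nominal visit timing and on P4 being taken as planned. The expected direction is a higher event proportion in women with a uterus, but the amount cannot be derived. A reader might infer that the E4 window should simply be cut off at the first P4 dose. The half-life argues against that as a replacement: events starting in the first post-E4 days may belong to E4, and findings from the EoT biopsy could acquire an onset date in the P4 period. The split should supplement the existing tables.

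**What to change.** In SAP 6.1 and 7.7.1.1:

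1. Keep the overall TEAE tables and add a phase flag by onset date. Phase 1 (E4) runs from the first E4 dose to the day before the first P4 dose, or to the EoT/early discontinuation visit if no P4 is taken. Phase 2 is the P4/follow-up period.
2. Show the overview, the AESI tables and the reproductive-system and abdominal-pain tables by hysterectomy status for each phase. Use phase 1 whenever the strata are compared.
3. Assign EoT-biopsy findings to phase 1 by sampling date.
4. Keep events that the investigator relates to E4 in the drug-related tables, whatever their phase.
5. Define *study drug* and Treatment Stop Date as E4 only, and align the listing wording in SAP 7.5.
6. Reconcile the end of AESI collection between Protocol 10.6 (EoT visit) and SAP 7.7.1.1 (follow-up visit).

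The cost is SAP wording and a few extra tables. Onset dates and P4 administration are already recorded, so no new data are needed.

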Samples for clinical blood tests will be taken during the Screening Period, at Visit 1 (baseline) and at the EoT (Visit 7 Efficacy Study part/Visit 6 Safety Study part). Samples will be processed in the central laboratory for analysis of the following parameters:

- Hematology: hematocrit, hemoglobin, erythrocytes, platelets, leukocytes, neutrophils, lymphocytes, basophils, eosinophils and monocytes
- Chemistry: urea, creatinine, total bilirubin, alkaline phosphatase, ALT, AST, sodium, potassium, chloride, bicarbonate, calcium, albumin, total protein, lactate dehydrogenase (LDH), LDH isoenzymes (I, II, III, IV, V), troponin, and blood glucose
- A urinary pregnancy tests may be performed at the discretion of the Investigator during the Screening visit and during the Randomization/Treatment allocation visit (Visit 1)

A sample for lipid and glucose parameters will be taken at washout visit or at screening visit and will be processed in the central laboratory for analysis of the following parameters:

- Lipid parameters: triglycerides, HDL-cholesterol, LDL-cholesterol, total cholesterol

- Glucose parameters: fasting glucose, glycated hemoglobin

The results of the above mentioned hematology, chemistry, lipid and glucose parameters will be analyzed during the trial on an ongoing basis and will be reported during the trial to the Investigator for safety monitoring. After review of the laboratory data, the Investigator must sign and date each laboratory report.

The laboratory will provide normal reference ranges for the laboratory results, and the laboratory report will flag all abnormal values. The Investigator will assess the clinical relevance of values outside the normal range and repeat, if needed, any clinically significant abnormal laboratory test.

Laboratory results should only be recorded and reported as AEs if they are considered as clinically significant, i.e., if they are associated with clinical symptoms, require active management, constitute SAEs or lead to discontinuation of treatment. As far as possible, the clinically significant abnormal laboratory value, as such, should not be recorded on the eCRF pages as an AE; rather, the etiology of the abnormality should be identified, and any clinical signs, symptoms or diagnoses which correspond to the laboratory abnormality should be recorded as an AE (Section 10.4.1).

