12.2. Baseline Values

Unless otherwise noted, baseline is defined as the last non-missing value recorded prior to the first dose of trial drug. Unscheduled visits will be used in the determination of baseline values, when applicable. This also applies to the primary efficacy variables derived from the VMS data collected in the subject diary, but on a weekly basis as described in the definition of the primary efficacy variables.

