### 3.3 Study Treatments and Assessments

After inclusion in the safety study part, the trial medication will be dispensed (see Section 9.4 in protocol) and subjects will take trial medication (20 mg E4, oral, once daily) on the day of treatment allocation visit (day 1 of week 1) and during the treatment period (Visit 1 - Visit 6). Subjects will be instructed to take the trial medication at approximately the same time each day. If a subject misses a dose, she will be instructed to take the dose as soon as she remembers. It is acceptable to take a dose up to 12 hours late. If taken more than 12 hours late the subjects will be instructed to omit dosing for that day and continue with the next dose as usual.

An overview of time windows for each visit is presented in [Appendix1](#); detailed description of procedures and assessments to be conducted during this study is summarized in [Appendix2](#).

---

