**Table 1: Derived Variables**

Variables	Formula																								
Demographic and Baseline Characteristics																									
Body mass index (BMI) (kg/m  )	weight (kg)/[height (m)] 																								
Study Treatment																									
Treatment Start Date	The date of first dose of study drug.																								
Treatment Stop Date	The date of last dose of study drug.																								
Duration of exposure (Days)	(Treatment Stop Date – Treatment Start Date) + 1																								
Treatment compliance (%)	100 x [(total number of tablets dispensed) – (total number of tablets returned)]/(duration of exposure in days)																								
Study Day	Prior to Treatment Start Date: Date of interest – Treatment Start Date  On or after Treatment Start Date: Date of interest – Treatment Start Date + 1																								
Study Week	
Study Week is defined as follows for the first 7 weeks
 
  
 Week	Start (Study Day)	End (Study Day)	
   
 1	1	7	
 
 2	8	14	
 
 3	15	21	
 
 4	22	28	
 
 5	29	35	
 
 6	36	42	
 
 7	43	49	
  
	Week	Start (Study Day)	End (Study Day)	1	1	7	2	8	14	3	15	21	4	22	28	5	29	35	6	36	42	7	43	49
Week	Start (Study Day)	End (Study Day)																							
1	1	7																							
2	8	14																							
3	15	21																							
4	22	28																							
5	29	35																							
6	36	42																							
7	43	49																							

Study Cycle	28-day period starting from Treatment Start Day
Adverse Events	
Adverse Event (AE) Start Day	Prior to Treatment Start Date: AE start date – Treatment Start Date  On or after Treatment Start Date: AE Start Date – Treatment Start Date + 1
AE Stop Day	Prior to Treatment Start Date: AE stop date – Treatment Start Date  On or after Treatment Start Date: AE stop date – Treatment Start Date + 1
AE Duration (Days)	(AE Stop Date – AE Start Date) + 1

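### SAP Table 1 cuts baseline off before the Visit 1 date, against protocol 12.2 and the SAP's own labels, and its TEAE rule leaves out events that start on the last-visit date

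*SAP*

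**What the plan says.** **Baseline.** Under SAP 6.1, Table 1, "Baseline is defined as the last non-missing value, including results from repeated and unscheduled measurements, prior to Treatment Start Date", subject to a proviso that allows exceptions noted elsewhere. Table 1 defines the Treatment Start Date as "The date of first dose of study drug", with no time of day. SAP 3.3 has the first tablet taken "on the day of treatment allocation visit (day 1 of week 1"), and protocol 10.1.6.1 agrees. Protocol 12.2 is different: "baseline is defined as the last non-missing value recorded prior to the first dose of trial drug".

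Elsewhere the SAP treats Visit 1 as baseline: in 3.1, in 7.6.1.5 for lipids and glucose, in the Visit 1 column heading of Appendix 2, and in Table 6, where an unscheduled Day 1 result is assigned to Visit 1 baseline. Protocol 10.4.5 does the same for routine laboratory tests: "Samples for clinical blood tests will be taken during the Screening Period, at Visit 1 (baseline) and at the EoT".

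**TEAE.** For an event with a known start date, Table 1 requires onset on or after the Treatment Start Date and that "AE Start Date is before the date of the last visit". The last visit is end of treatment (EoT), early discontinuation or, for non-hysterectomized women, the follow-up visit. Protocol 10.4.1 runs the TEAE period from first intake until the last visit and does not say whether that day counts.

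SAP section 8 lists three changes from the protocol, all to analysis sets. Neither of these rules is among them.

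**The concern.** Both rules use a strict date comparison at a boundary where the trial schedules assessments.

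At the start, the Visit 1 measurements share their date with the first dose, so a program that follows Table 1 discards them and goes back to screening. Changes in vital signs and in routine laboratory results belong to the primary endpoints of this part. For blood pressure, the screening reading is the one tested against the eligibility limits; protocol 10.4.3 allows a repeat and uses the last reading. A change measured from it could include regression to the mean, and this single-arm part has no control to show that.

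At the end, TEAE frequency is the first primary endpoint, and the strict bound can only lower it. For hysterectomized women the last visit is EoT or early discontinuation. In the schedule this is the only post-baseline physical examination, gynecological examination and ECG. Protocol 10.4.2 and 10.4.4 require clinically significant findings from these to be recorded as AEs. A finding dated to that visit cannot be a TEAE, although protocol 10.1.6.6 places the last dose on the evening before.

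**Working it through.** The plan gives no figure to reproduce. The check applies the date rules as written.

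**1. Does Visit 1 qualify as baseline?** The rule is: assessment date < Treatment Start Date. Visit 1 date = first-dose date = Treatment Start Date, which is Study Day 1, so the condition is false. A screening value at Day -28 qualifies, as does one at Day -56. Under protocol 12.2 a Visit 1 value qualifies, because protocol 10.1.6.1 has drug dispensed after treatment allocation at that visit.

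**2. How far back does baseline move?** Screening lasts up to 4 weeks, 4 × 7 = 28 days. SAP Appendix 2, footnote u, allows 8 weeks, 8 × 7 = 56 days. (The footnote to SAP Table 5 still says 6 weeks.)

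**3. Which lipid and glucose variables have an earlier scheduled value?** SAP 7.6.1.5 lists 6 lipid + 4 glucose = 10 variables. The inclusion panel in protocol 10.4.5 has triglycerides, HDL, LDL and total cholesterol, and then "Glucose parameters: fasting glucose, glycated hemoglobin": 4 + 2 = 6. The total/HDL cholesterol ratio can be derived, giving 7. The remaining 10 − 7 = 3 are lipoprotein(a), insulin and HOMA-IR.

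**4. MENQOL.** The change scores are 4 domains + 1 total = 5. SAP 3.1 and Appendix 2 place the full form first at Visit 1, and Appendices 2 and 3 show the modified form as the screening form. SAP 7.6.1.6.1, however, says the modified form is completed at baseline. With the literal Table 1 rule, the baseline is then either absent or the screening form.

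**5. Which variables do other SAP passages protect?**
- Lipids, glucose and MENQOL: Visit 1 is named as baseline in 3.1, and for lipids and glucose also in 7.6.1.5.
- Hematology and chemistry: Table 6 maps Day 1 to baseline.
- Blood pressure: only the general labels in 3.1 and Appendix 2 apply. Table 7, which covers vital signs, has no Day 1 row, and 7.7.1.3 names no baseline visit.
- Measures scheduled before treatment only at screening (physical, gynecological and breast examination, ECG, mammography, ultrasound, biopsy, body weight): Table 1 works unchanged.

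**6. The TEAE boundary.** The rule is: Treatment Start Date ≤ onset < last-visit date. Take a last visit on Day 365:

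| Onset | SAP rule | Last-visit date included |
|---|---|---|
| Day 364 | TEAE | TEAE |
| Day 365 | not a TEAE | TEAE |
| Day 366 | not a TEAE | not a TEAE |

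This is not a last-dose cut-off. For non-hysterectomized women the window runs to Visit 7, about 14 + 10 = 24 days after EoT. Nor is it uniform: events with an unknown start date have no upper limit in Table 1.

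**7. Who is exposed to the TEAE boundary?** At most about 200 hysterectomized women, plus non-hysterectomized women without a Visit 7. Protocol 8.1 expects 50% dropout by 12 months. If that applied equally to hysterectomized women (an assumption), about 200 × 0.5 = 100 would reach the scheduled EoT visit. Others are exposed only if they attend an early discontinuation visit.

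**The case against.** The strongest reply is that the intent is plain and the text largely repairs itself. The proviso in Table 1 lets the Visit 1 labels prevail, and the variables with no earlier value would show empty change columns, so that error would be noticed. Most of this stands. It does not cover blood pressure: a screening value exists, so a literal program would run without warning.

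Five stronger readings are tempting, and the documents do not support them:

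- *The baseline rule cannot be followed at all.* It works for everything measured before treatment only at screening.
- *Laboratory change and shift tables will run from screening values.* The Day 1 row of Table 6 is written for unscheduled results, but if those count as baseline, the scheduled Visit 1 sample should too.
- *All five MENQOL scores lose their baseline.* SAP 7.6.1.6.1 offers the modified form. Whether it yields the domain scores cannot be judged, because the forms are not shown.
- *The TEAE rule contradicts the protocol.* Protocol 10.4.1 leaves the last-visit day open, so silence in SAP section 8 does not show an undeclared change on this item.
- *Blood pressure changes will be biased.* Eligibility is reviewed again at Visit 1, where vital signs are also taken, and the documents do not exclude that the Visit 1 reading is checked too. Regression to the mean is a possibility of unknown size.

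It is also fair to say that the TEAE loss is one calendar date and depends on how onset is dated, for which the documents give no rule. Examination and ECG findings remain in the shift tables, and all AEs remain in the listings.

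**Conclusion.** Both rules need correcting. The baseline wording departs from protocol 12.2 without being declared and conflicts with the SAP's own labels, although pre-dose Visit 1 is very probably meant. The clearest remaining exposure is blood pressure. If Table 1 is programmed literally, 3 of 10 lipid and glucose variables have no scheduled earlier value, and the MENQOL baseline is absent or taken from a different form.

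The TEAE wording excludes any known onset on the last-visit date. The loss is confined to that date and to TEAE-based counts, and it matters mainly where EoT or early discontinuation is the last visit. The figure of about 200 hysterectomized women is an upper bound on those exposed, not a count of lost events.

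A reader might infer a loss of adverse events of special interest as well. That depends on an unreconciled conflict: protocol 10.6 ends their collection at EoT, SAP 7.7.1.1 at the follow-up visit.

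No effect on any result can be computed, because the documents give no event rates, onset dates or blood pressure variability. The conclusions rest on a literal reading of Table 1 and on the first dose being taken on the Visit 1 date, as both documents require.

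**What to change.** Change two entries in SAP Table 1 and add one sentence to 7.6.1.6.1:

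- Baseline: the last non-missing value before the first dose of study drug, with Visit 1 (Day 1) assessments taken as pre-dose.
- TEAE, known start date: onset on or after the Treatment Start Date and on or before the date of the last visit.
- MENQOL: the full form at Visit 1 is the baseline for change scores; the modified form is for screening only.

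These are text edits that need no new data. The first restores protocol 12.2. With the second, the TEAE count can only stay the same or rise. The conflict over when collection of adverse events of special interest ends should be reconciled in the same revision.
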